9.2.2. Serious Adverse Event Reporting and Documentation Requirements

Any SAE must be reported (see [Section 9.1.6](#)) by the Investigator if it occurs from the time of signed consent through 30 days after the last dose of study drug (KZR-616 or placebo) if the patient is withdrawn from the study early or at the SFU, whether or not the SAE is considered to be related to the investigational product. After the reporting period, SAEs should be reported if the Investigator assesses the event to be related to study drug. An SAE report consists of the SAE form, provided separately, along with requested additional source documentation as considered necessary.

Serious adverse events that occur during the reporting period must be reported by the Investigator via entry of data into the eCRF within 24 hours from the point in time when the

Investigator becomes aware of the SAE. This will trigger an email notification to the Serious Adverse Event Reporting e-mail address (see below) that an SAE has occurred. If the EDC system is down or unavailable, a copy of the SAE form should be completed and emailed or faxed by the Investigator to the Serious Adverse Event Reporting e-mail address or dedicated fax (see below) within 24 hours from the point in time when the Investigator becomes aware of the SAE. Once the EDC system is available, the SAE should be entered in the eCRF. The Investigator should not wait for additional information to fully document the SAE before reporting it, though additional information may be requested. Requested source documentation (ie, relevant laboratory results, hospital case records, or autopsy reports) that is considered necessary should be provided separately to the Serious Adverse Event Reporting e-mail address using a cover sheet.

Contact Information:

Serious Adverse Event Reporting E-mail: [REDACTED]

Fax: [REDACTED]

Instances of death, congenital abnormality, or an event that is of such clinical concern as to influence the overall assessment of safety, if brought to the attention of the Investigator at any time after cessation of study drug administration and linked by the Investigator to this study, should be reported to the study monitor.

The Sponsor and/or designee will promptly notify all relevant Investigators and the regulatory authorities of findings that could adversely affect the safety of patients, impact on the conduct of the study, or alter the DMC/IRB/IEC approval/favorable opinion of the study. In addition, the Sponsor or designee, will expedite the reporting of all adverse reactions that are both serious and unexpected to all concerned Investigators, to the DMC/IRBs/IECs where required, and to the regulatory authorities.

9.3. Pregnancy Reporting

Pregnancy occurring during a clinical investigation must be reported to safety within 24 hours and entered into the EDC. The outcome of a pregnancy should be followed up carefully and any abnormal outcome of the mother or the child should be reported. This also applies to pregnancies following the administration of the investigational product to the father prior to sexual intercourse. Infants should be followed for a minimum of 8 weeks and all findings should be reported to the Sponsor. Study drug is to be discontinued immediately upon Investigator knowledge of the pregnancy and reported as per [Section 8.2](#).

If the outcome of the pregnancy meets a criterion for immediate classification as an SAE—spontaneous abortion (any congenital anomaly detected in an aborted fetus is to be documented), stillbirth, neonatal death, or congenital anomaly—the Investigator should repeat the procedures for expedited reporting of SAEs as outlined above.

Full details will be recorded on the withdrawal page of the eCRF, or an SAE report will be completed if the patient has completed the study.

9.4. New or Worsening Disease Manifestations

New or worsening manifestation(s) of DM or PM should not be recorded as AEs unless they are assessed as serious.

9.5. Adverse Events of Special Interest

Adverse events of special interest should be reported within 24 hours using the AE eCRF as per [Section 9.1.6](#). No additional reporting will be required unless they become SAEs.

9.5.1. Systemic Injection Reactions

Systemic injection reactions have been observed with KZR-616 and other proteasome inhibitors and are considered AESIs.

Systemic injection reactions have included a number of signs and symptoms including fever, chills, myalgia, facial swelling or flushing, vomiting, weakness, hypotension, chest tightness, and shortness of breath, as well as abnormalities in laboratory values (eg, creatinine, transaminases). The relative roles of the immunoproteasome versus constitutive proteasomes to these specific events are not known. Therefore, terms such as eg, the NCI-CTCAE or Medical Dictionary for Regulatory Activities (MedDRA) terms of ‘injection related reaction,’ ‘cytokine release syndrome,’ ‘systemic immune activation,’ ‘drug hypersensitivity,’ ‘hypersensitivity reaction,’ or ‘allergic reaction’ should not be used. Instead, each sign or symptom should be recorded as an individual AE with its own level of severity, even if multiple signs or symptoms occur.

Management of systemic injection reactions is described in [Section 6.1.3](#).

9.5.2. Thrombotic Microangiopathy

Cases of TMA, including TTP and HUS have been described with the nonspecific proteasome inhibitors, bortezomib, carfilzomib, and ixazomib, and are considered AESIs. One SAE of TMA has also been reported in a patient with SLE receiving KZR-616. While SLE itself is a risk factor for TMA, the contribution of KZR-616 to the event could not be ruled out. The clinical presentation of TMA typically includes fever, microangiopathic hemolytic anemia (with schistocytes on blood smear), thrombocytopenia, renal failure, purpura, and neurological manifestations. Patients should be monitored for signs and symptoms of TTP/HUS. If the diagnosis is suspected, interrupt treatment with study drug and evaluate (refer to [Section 8.1.2](#)). Missed doses should be addressed as per [Section 6.1.4.2](#). If the diagnosis of TTP/HUS is excluded, study drug may be resumed. If the diagnosis is confirmed, study drug must be permanently discontinued (refer to [Section 8.2](#)).

9.6. Unexpected Adverse Reactions

9.6.1. Unexpected Adverse Reaction Definition

An unexpected adverse reaction is any untoward and unintended response that is related to the administration of the study drug at any dose that is not consistent with the applicable

product information (eg, IB for an unauthorized investigational medicinal product or prescribing information for an authorized product).

All suspected unexpected serious adverse reactions (SUSARs) will be subject to expedited reporting. The Sponsor or designee shall ensure that all relevant information about a SUSAR that is fatal or life-threatening is reported to the relevant competent authorities and IRB/IEC within 7 days after knowledge by the Sponsor of such a case and that relevant follow-up information is communicated within an additional 8 days. All other SUSARs will be reported to the relevant competent authorities and IRB/IEC within 15 days after knowledge by the Sponsor of such a case. All Investigators should follow up SUSARs until the event is resolved or until, in the opinion of the Investigator, the event is stabilized or determined to be chronic. Post study SUSARs that occur after the patient has completed the clinical study must be reported by the Investigator to the Sponsor.

9.7. Data Monitoring Committee

To enhance the safety and integrity of the study data, a study-specific DMC will be established for interim safety monitoring. The specific responsibilities and composition of the DMC are outlined in a separate DMC Charter. In addition, the details of outputs provided for the meetings will be referenced in the separate document.

10. STATISTICAL ANALYSES

A detailed Statistical Analysis Plan (SAP) will be prepared for approval by the Sponsor prior to performing any unblinded analysis for presentation to personnel designated as being blinded to the randomization.

10.1. Sample Size Calculation

Prior summary statistics on change from Baseline in TIS score are not available. Hence, statistical power is quantified via standardized effect size (mean difference divided by pooled standard deviation [SD]). A sample size of 24 patients has 80% power to yield a statistically significant ($\alpha=0.05$ 2-sided) improvement from Baseline if the true underlying effect size is 0.6 (90% power if true effect size is 0.7). The minimum observed effect size that would yield statistical significance is 0.42. This level of statistical precision is thought to be adequate for this initial trial of KZR-616 in PM and DM.

10.2. Analysis Populations

The Safety Analysis Set consists of all patients who receive at least 1 dose of the study drug.

The Full Analysis Set (FAS) consists of all patients who receive at least 1 dose of the study drug and who have a Baseline and post-Baseline observation. This is the primary efficacy analysis set for the study.

The Per Protocol Analysis Set consists of all patients in the FAS, excluding those identified as having relevant protocol deviations.

The PK Analysis Set consists of all patients who received at least 1 dose of KZR-616 and for whom the PK data are considered sufficient. Since this is a Phase 2 trial, all analyses and summaries will be based on the actual test treatment the respective patients received.

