4. PATIENT SELECTION AND ENROLLMENT

4.1. Number of Patients

Approximately 24 patients are planned for enrollment. It is anticipated that 40 patients will be screened to achieve 24 patients enrolled.

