6.1.4.2. Missed Doses

Doses should be administered within the visit windows as per the Schedules of Assessments ([Section 7.1](#)). Any doses administered outside of the visit window will be considered a protocol deviation, but if necessary to avoid missing a dose, doses can be administered up to 3 days from the date of scheduled administration per [Section 7.1](#) with a minimum of 4 days required between doses.

Patients who do not fulfill Dosing Criteria ([Section 6.1.1](#)) or who meet Individual Patient Stopping Rules ([Section 8.1.2](#)) may miss up to 2 consecutive doses, or patients may miss up to 4 total doses for any reason (eg, AE, scheduling, emergency). Upon resumption of dosing, subsequent doses should be timed according to the original dosing schedule based on Day 1. If more than 2 consecutive doses or more than 4 total doses were missed, then the patient should be discussed with the Medical Monitor to evaluate if KZR-616 should be discontinued. Any dose modifications should be discussed with the Medical Monitor and documented in the eCRF as per [Section 9.1.4](#). Patients who are discontinued for missed doses should have their discontinuation per [Section 8.2](#) recorded in the eCRF based on the reason the doses were missed, eg, AE, protocol noncompliance.

If study medication is permanently discontinued due to an AE, the planned assessments (see Schedule of Assessments) should continue for the protocol specified time period.

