8.2. Early Withdrawal of Patients from the Study

In accordance with applicable regulations, a patient has the right to withdraw from the study, at any time and for any reason, without prejudice to future medical care.

Patients may be withdrawn from the study for the occurrence of any of the following reasons:

- Patient request/informed consent withdrawn due to an AE
- Patient request/informed consent withdrawn due to reasons other than an AE
- Patient becomes pregnant
- Adverse event (whether or not related to the study drug) that precludes further participation in the study in the judgment of the Investigator and/or Sponsor
- Protocol noncompliance in the judgment of the Investigator and/or Sponsor
- Lost to follow-up
- The Investigator or Sponsor considers that it is in the patient's best interest for the patient not to continue participation in the study
- Administrative decision by the Investigator or Sponsor.

Patients who withdraw from the study will not be replaced.

Patients are free to withdraw from the study at any time without providing reason(s) for withdrawal and without prejudice to further treatment. The reason(s) for withdrawal will be documented in the eCRF. If a patient withdraws consent, all samples obtained will be retained for analysis unless the patient confirms that he or she wishes the samples to be discarded.

Patients who withdraw from the study prior to W32 will be requested to undergo the ETV procedures within 7 days of the withdrawal, and all patients who withdraw from the study prematurely will be requested to return for the SFU Visit 9 weeks (to perform W40 visit procedures) after receipt of their last dose of the study drug as per [Table 4](#). Patients withdrawing from the study treatment will be encouraged to complete the same final evaluations as patients completing the study according to this protocol, particularly safety evaluations. The primary reason for withdrawal will be identified and recorded on the appropriate eCRF, along with the date of withdrawal.

Reasonable efforts will be made to contact patients who are lost to follow-up. These efforts must be documented in the patient's file.

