10.3. Efficacy Analysis

The primary endpoint is mean change from start to end of KZR-616 treatment in TIS.² For the continuous efficacy parameters, within-patient changes will be analyzed as follows:

- (1: primary) by comparing the Baseline and post Baseline observations within patients for the KZR-616 treatment periods combined, ie, W16 versus W0 for patients allocated to the randomized treatment sequence KZR-616 followed by placebo and W32 versus W16 for patients allocated to the randomized treatment sequence placebo followed by KZR-616, combined;
- (2: secondary) by comparing the change from Baseline in Treatment Period 1 between treatments, ie, change from W0 to W16 for patients allocated to the randomized treatment sequence KZR-616 followed by placebo versus change from W0 to W16 for patients allocated to the randomized treatment sequence placebo followed by KZR-616; and
- (3: exploratory) by comparing the last response on test treatment between treatments via a crossover design analysis, ie, W16 for patients allocated to the randomized treatment sequence KZR-616 followed by placebo and W32 for patients allocated to the

randomized treatment sequence placebo followed by KZR-616, combined, versus W16 for patients allocated to the randomized treatment sequence placebo followed by KZR-616 and W32 for patients allocated to the randomized treatment sequence KZR-616 followed by placebo, combined.

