The rationale for this priority order is as follows. The usual crossover analysis for this design is prespecified as exploratory since it is unknown whether that analysis would be confounded by carryover effect. In order to maximize the precision for assessment of KZR-616 effect, it is assessed primarily via all patients' Baseline versus post-Baseline KZR-616 assessment and secondarily by the Treatment Period 1 between-treatment comparison. Summary statistics, including 95% confidence intervals, will be provided for each treatment for each of the 3 types of analysis. Within-patient changes will be analyzed via paired t-tests and corroborated by signed rank tests. Between-patient differences will be analyzed via analysis of covariance, with Baseline as a covariate. The crossover analysis will be via a mixed-model repeated-measures analysis. Normality will be assessed graphically and via the Shapiro-Wilk statistic. If substantial departure from normality is observed, transformations, eg, natural log and rank, will be explored. P values will be 2-sided with at the type 1 error level 0.05.

Binary endpoints will be summarized by counts and percent and 95% confidence intervals via Clopper-Pearson method. Additional analyses will be specified in the SAP.

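### The primary analysis set is not aligned with an endpoint that, in Arm B, only begins at Week 16, and the stated power allows for no losses in either arm

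*Combined protocol and SAP*

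**What the plan says.** Section 10.2 names the Full Analysis Set (FAS) as the primary efficacy set. It consists of patients "who receive at least 1 dose of the study drug and who have a Baseline and post-Baseline observation". Section 3.1 defines Baseline as Day 1 of Week 0. Table 1 (Section 6.1) gives Arm B placebo through Week 15 and its first KZR-616 dose at Week 16. In Section 10.2 only the PK Analysis Set requires a dose of KZR-616. The same section says that all analyses follow the treatment actually received.

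The primary endpoint (Sections 2.2.1 and 10.3) is the mean TIS change over KZR-616 treatment. Analysis (1) in Section 10.3 pools the KZR-616 periods of both arms. For Arm B it uses "W32 versus W16 for patients allocated to the randomized treatment sequence placebo followed by KZR-616, combined".

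Section 6.1.4.2 says that after permanent discontinuation for an adverse event the "planned assessments (see Schedule of Assessments) should continue for the protocol specified time period". Section 8.2 says: "Patients who withdraw from the study will not be replaced".

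On size, Section 4.1 says "Approximately 24 patients are planned for enrollment", and Section 10.1 says "A sample size of 24 patients has 80% power to yield a statistically significant" result at effect size 0.6. It adds 90% power at 0.7 and a minimum significant observed effect of 0.42.

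**The concern.** The set and the endpoint start from different points. Every dosed Arm A patient has had KZR-616 and has a KZR-616 start value at Week 0. An Arm B patient meets the FAS definition with one placebo dose, a Week 0 value and, say, a Week 4 value. That patient has had no KZR-616 and has neither of the values that the primary contrast needs.

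The text does not say clearly what happens to such patients. Two statisticians could build different primary sets from it, and the difference would fall on one arm only. For the responder proportions, Section 10.3 gives the interval method but no denominator other than the FAS.

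The second issue is separate. The number used for power equals planned enrolment, over two consecutive 16-week periods, with no replacement. Any patient without a usable pair, in either arm and for any reason, takes the trial below its stated figures.

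**Working it through.** **1. Is a patient who never received KZR-616 in the primary analysis?** Take an Arm B patient who permanently stops blinded drug for an adverse event in Period 1 and stays under assessment.

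- FAS definition (Section 10.2): met, since one placebo dose and a post-Baseline value suffice.
- Data: under Section 6.1.4.2 both Week 16 and Week 32 values can exist.
- Arm B contrast (Section 10.3): defined by allocation, so Week 32 minus Week 16 enters as a KZR-616 change.
- As-received rule (Section 10.2), the restriction to KZR-616 treatment periods (Section 10.3) and the endpoint wording: each points to leaving the patient out.

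The passages give two answers. An Arm B patient who leaves before Week 16 is a different case: there is no Week 16/Week 32 pair, so nothing enters the paired mean. Only the denominator of the responder proportions is then in doubt.

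**2. Reproducing the stated power.** Inputs: n = 24, standardized effect d = 0.6 or 0.7 (Section 10.1); two-sided alpha 0.05 and a paired t-test (Section 10.3). Power comes from the noncentral t distribution with n − 1 degrees of freedom and noncentrality d√n. The minimum significant observed effect is t(0.975, n − 1)/√n.

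- d = 0.6: noncentrality 0.6 × √24 = 2.94; power 80.4%.
- d = 0.7: noncentrality 0.7 × √24 = 3.43; power 90.7%.
- Threshold: 2.069/4.899 = 0.422.

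All three match the plan.

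**3. Fewer evaluable pairs.** The documents give no loss rate, so the losses below are assumptions.

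| Evaluable pairs | Lost | Power at 0.6 | Power at 0.7 | Minimum significant effect |
|---|---|---|---|---|
| 24 | 0 | 80.4% | 90.7% | 0.422 |
| 23 | 1 | 78.5% | 89.4% | 0.432 |
| 22 | 2 | 76.5% | 87.9% | 0.443 |
| 20 | 4 | 72.1% | 84.4% | 0.468 |
| 18 | 6 | 67.0% | 79.9% | 0.497 |

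The smallest n that gives 80% at 0.6 is 24, and so is the smallest that gives 90% at 0.7.

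**4. If never-exposed patients were kept instead.** Assume that k of the 24 have no true change and the rest have effect 0.6 with SD 1. The mean effect is 0.6 × (1 − k/24), which is 0.55 for k = 2 and 0.50 for k = 4. With p = k/24, the SD is √(1 + 0.36p(1 − p)) if these patients vary as much as the others, or √((1 − p) + 0.36p(1 − p)) if a change of exactly zero is imputed. Treating the mixture as approximately normal, power is 72.1% or 75.7% for k = 2, and 62.9% or 70.4% for k = 4. For the same numbers, exclusion gives 76.5% and 72.1%.

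**5. Responder proportion.** Assume two Arm B patients never reach KZR-616 and 10 patients respond. The result is 10/24 = 42% (Clopper-Pearson 95% CI 22 to 63) or 10/22 = 45% (24 to 68), depending on the denominator.

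**The case against.** The best defence is that inclusion of never-exposed patients is not the natural reading. The endpoint is defined on KZR-616 treatment, analysis (1) is confined to KZR-616 periods, and Section 10.2 ties every analysis to treatment received. Belonging to the FAS does not by itself create an evaluable pair. That stands. A reader might infer that the plan as written dilutes the KZR-616 mean, but the documents do not support that. They support an unresolved conflict, realistic mainly for Arm B patients who stop for an adverse event on placebo and remain under assessment, and no frequency for that can be drawn from the text.

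Section 10.3 also uses the word Baseline for Arm B's Week 16 value, so reading the FAS as Week 0 plus any later value is not beyond dispute. It does follow from the definition in Section 3.1, and the two uses need to be reconciled in any case.

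The power effect is gradual: one loss costs about two points. Effect size 0.6 is notional, because Section 10.1 says that no prior TIS change data exist, and the plan calls the precision adequate for a first trial. This limits the importance of the point, but the stated figures still have no margin.

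Detail is deferred to a SAP still to be prepared (Sections 10 and 10.3). It can resolve the ambiguity, but nothing in the supplied text does so yet. The synopsis adds to the confusion: under the Per Protocol label it gives the definition that Section 10.2 gives for the PK set.

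**Conclusion.** The point holds in two separate parts.

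First, the primary set does not match the primary endpoint for Arm B. The allocated-sequence contrast, together with continued assessment, conflicts with the as-received rule and the KZR-616-period wording. This is an ambiguity to settle before unblinding, not a demonstrated bias. On the assumed example the effect on the responder proportion is small (42% versus 45%).

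Second, the stated 80%, 90% and 0.42 hold only if all 24 planned patients give a usable pair. With an assumed 20 to 22 pairs, power is 72% to 77% at 0.6 and 84% to 88% at 0.7, and the threshold is 0.47 to 0.44.

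Three further inferences should be resisted. Section 10.1 says only 24 patients; it does not count anyone dosed with any study drug. Dilution and lost sample size are alternatives for a given patient and cannot be added together. The power shortfall is not specific to Arm B, since losses during KZR-616 treatment in either arm have the same effect.

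**What to change.** - **Analysis set.** For analysis (1) and every endpoint measured over KZR-616 treatment, use patients with at least one KZR-616 dose and a value at KZR-616 start (Week 0 in Arm A, Week 16 in Arm B). State the rule for a missing end value. Keep the current FAS for the Period 1 comparison.
- **Consistency.** Reconcile the allocated-sequence wording in Section 10.3 with the as-received rule in Section 10.2, the two uses of Baseline, and the synopsis definition of the Per Protocol set.
- **Reporting.** Give, by arm, the number who never reached KZR-616.
- **Section 10.1.** Restate power and the threshold for a plausible evaluable number (for example 20 to 22), or state that the figures assume no losses.

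The cost is wording in Sections 10.1 to 10.3, the synopsis and the SAP, with no added patients. There are two downsides. The stated power becomes slightly less favourable, and the primary set becomes conditional on Arm B patients getting through 16 weeks of placebo, a selection after randomization in one arm; the count by arm makes that visible. The change does not restore power. Keeping 24 evaluable pairs at an assumed 10% loss would need 24/0.9 = 26.7, so 27 enrolled.
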